7.1 DISCONTINUATION OF STUDY INTERVENTION/EXPERIMENTAL MANIPULATION

When a subject discontinues from any element of RE-PACT (action planning, texting, coaching), but not from the study, remaining study procedures will be completed as indicated by the study protocol.

The data to be collected at the time of study intervention discontinuation will include the following:

- The reason(s) for discontinuing the participant from the intervention, and methods for determining the need to discontinue
- If the participant is due to complete assessments within 2 weeks of being discontinued from the study intervention, those assessments will be administered at the time of discontinuation; if the next scheduled assessments are more than 2 weeks from the discontinuation date, the discontinued participant will wait for the next scheduled assessment. Thereafter, the participant will be included in all future scheduled assessments, even though not participating in the intervention.

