7.2 PARTICIPANT DISCONTINUATION/WITHDRAWAL FROM THE STUDY

Participants are free to withdraw from participation in the study at any time upon request.

An investigator may discontinue a participant from the study for the following reasons:

- Significant study intervention non-compliance, unless varying compliance is an aspect of the study objectives
- Lost-to-follow up; unable to contact subject (see **Section 7.3, Lost to Follow-Up**)
- The participant meets an exclusion criterion (either newly developed or not previously recognized) that precludes further study participation
- If a subject is no longer a part of the complex care program at the UW or UCLA, their enrollment in the study will be discontinued.

The reason for participant discontinuation or withdrawal from the study will be recorded on the Discontinuation/Withdrawal Case Report Form (CRF). Subjects who sign the informed consent form and are randomized but do not receive the study intervention may be replaced. Subjects who sign the informed consent form, and are randomized and receive the study intervention, and subsequently withdraw, or are discontinued from the study, will not be replaced.

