7.3 LOST TO FOLLOW-UP

A participant will be considered lost to follow-up if they are no longer a member of the clinical program, or if they fail to respond to 3 consecutive months of texting, or 3 monthly assessments in a row, and study staff are unable to contact the participant after at least 3 attempts.

The following actions will be taken if a participant fails to respond:

- The site will attempt to contact the participant, counsel the participant on the importance of maintaining the assigned schedule and ascertain if the participant wishes to and/or should continue the study.
- Before a participant is deemed lost to follow-up, the investigator or designee will make every effort to regain contact with the participant (where possible, 3 telephone calls and, if necessary, a certified letter to the participant's last known mailing address or local equivalent methods). These contact attempts will be documented in the participant's study file.
- Should the participant continue to be unreachable, he or she will be considered to have withdrawn from the study with a primary reason of lost to follow-up.

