9.3 POPULATIONS FOR ANALYSES

Given that the intervention being tested requires parent adherence to recommendations to achieve success, we will use an intention-to-treat analysis approach.

While we anticipate that the intervention and control groups will be similar due to random assignment, we will adjust for any variables in our analysis that are not equal between the groups given the small sample size. In addition, we will analyze for any effect of primary home language on the study outcomes, as this may affect families' ability to navigate systems of care in the U.S.

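### Leaving the complex care program ends study follow-up without asking whether the family can still be followed, while stopping the intervention does not; the two rules, and the drop-out measure, need reconciling.

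*Combined protocol and SAP*

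**What the plan says.** Four parts of the protocol bear on this.

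- **Section 7.2** lists reasons for discontinuing a participant from the study. One bullet covers a subject who is "no longer a part of the complex care program at the UW or UCLA, their enrollment in the study will be discontinued". It stands apart from the bullet on subjects who cannot be contacted and sets no condition on reachability or willingness. The list opens by saying what an investigator may do, while this bullet says what will happen.
- **Section 7.3** says: "A participant will be considered lost to follow-up if they are no longer a member of the clinical program". Two non-response limbs follow (texting and monthly assessments), and the sentence closes with "and study staff are unable to contact the participant after at least 3 attempts".
- **Section 7.1** treats families who stop some or all of RE-PACT but stay in the study differently: "the participant will be included in all future scheduled assessments, even though not participating in the intervention".
- **Section 9.3** states that "we will use an intention-to-treat analysis approach", with no further definition.

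The primary-endpoint table in section 3 has a row for loss and drop-out. It covers active and passive drop-out before 6 months as a share of those enrolled, with success below 10%. It does not say whether leaving the program counts.

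**The concern.** Leaving a clinic is not withdrawal of consent, and it does not by itself make a family unreachable. Sections 4.1 and 8.1 allow questionnaires by telephone or electronic link, and parent report already covers use of care. Some outcome information could therefore be obtained after departure, yet the rule as written stops collecting it. The protocol gives no reason for treating these families differently from those who stop the intervention.

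Two things are at stake. The first is the effect estimate: outcomes go missing after an event that occurs after randomisation and that could be related to health or to arm. The second is a primary acceptability measure with a tight limit. If program departures are counted, a change of clinic is scored in the same way as a family that drops out of the study.

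**Working it through.** **1. The rules side by side**

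| Event | Section | Later assessments | Reachability asked? |
|---|---|---|---|
| Stops the intervention, stays in study | 7.1 | Continue | Not applicable |
| Leaves the program | 7.2 | End with enrolment | No |
| Leaves the program | 7.3 | Loss to follow-up | Depends on how the sentence is read |

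In section 7.3 the word *if* is repeated before the non-response limbs. The plain reading is therefore that departure alone suffices and that the closing contact condition belongs to non-response. The condition could also be read as covering every limb. Section 7.2 ends enrolment on either reading.

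Two related points appear in the same comparison. Section 4.1 admits children from a complex care or a cerebral palsy program, while section 7.2 names only the former. The schedule in section 1.3 places texting and monthly assessments under the intervention arm only, so for controls departure is the one limb of section 7.3 that clearly applies.

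**2. The drop-out criterion**

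Inputs from the documents: 90 enrolled, in waves of 10, 20 and 60 (section 9.2); success below 10% (section 3); measures reviewed between waves, with adjustments where one falls short (section 8.1).

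- All participants: 8/90 = 8.9% passes and 9/90 = 10.0% does not, so at most 8 are allowed.
- By wave, the most that stays below 10% is 0 of 10, 1 of 20 and 5 of 60. One leaver in wave 1 gives 1/10 = 10%, a miss.

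The documents give no departure rate. Assuming 4 other drop-outs and that leavers count:

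- 3 leavers: (4 + 3)/90 = 7.8%, pass.
- 7 leavers: (4 + 7)/90 = 12.2%, fail.
- Leavers not counted: 4/90 = 4.4%, pass.

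For the chance of failing, let *a* be other drop-out and *d* departure, both assumed and independent. Then q = 1 − (1 − a)(1 − d), and the failure probability is P(X ≥ 9) with X binomial(90, q). For example, a = 5% and d = 3% give q = 1 − 0.95 × 0.97 = 7.85%.

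| Other drop-out | d = 0 (or not counted) | d = 2% | d = 3% | d = 5% |
|---|---|---|---|---|
| 5% | 3.6% | 16.8% | 27.4% | 52.0% |
| 7% | 17.8% | 40.4% | 52.5% | 73.5% |

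**3. Information lost on the clinical outcome**

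Full follow-up is 90 × 6 = 540 person-months. At the one severe illness per year given in section 9.2, that is 540/12 = 45 expected events before any intervention effect. Assume leavers go, on average, at 3 months.

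- 3 leavers lose 3 × 3 = 9 person-months (9/540 = 1.7%), about 9/12 = 0.75 events.
- 7 leavers lose 7 × 3 = 21 person-months (21/540 = 3.9%), about 21/12 = 1.75 events.
- If a complete-case analysis drops leavers altogether, 7 leavers cost 7 × 6 = 42 person-months (42/540 = 7.8%), about 42/12 = 3.5 events.

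**4. Possible bias**

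A simulation used gamma-Poisson counts with overdispersion 1 and 1/12 events per month, a true rate ratio (intervention over control) of 1, and departure uniform over 6 months.

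| Departure, intervention vs control | Relation to risk | Person-months | Complete case | Full follow-up |
|---|---|---|---|---|
| 5% vs 5% | Strong | 0.99 | 1.00 | 1.00 |
| 3% vs 15% | None | 1.00 | 1.00 | 1.00 |
| 5% vs 10% | Strong | 1.02 | 1.04 | 1.00 |
| 3% vs 15% | Strong | 1.04 | 1.10 | 1.00 |

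Bias appears only when departure is related to both arm and risk. These departure rates are assumptions, so the table illustrates the mechanism and does not estimate its size in this trial.

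**The case against.** The strongest defence is that program care is more than a recruitment source. It is an entry condition, it is the control condition, and its clinical team creates the action plans. The primary clinical outcome is defined by discharge diagnosis, and the steroid outcome by dose and duration, all with chart review in mind. Once a child is treated elsewhere, charts at the two sites may miss events, and a telephone questionnaire cannot match chart abstraction. Ending enrolment at that point has a plausible rationale in a pilot that is declared not to be powered for efficacy. The point about chart review stands, and it is a real cost of the fix. It does not justify collecting nothing: caregiver report, backed by records where the authorisation allows, tells more than a missing outcome.

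Other parts of the defence limit what can be claimed.

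- A reader might infer that the rule breaks intention-to-treat. The documents do not support that. Nothing moves leavers out of their arm, the person-month denominator in section 9.4.3 can keep time before departure, and multiple imputation is planned as a sensitivity analysis against complete case.
- A reader might infer that leavers are known to be reachable. No section says so; section 7.2 simply does not ask.
- A reader might infer that the drop-out measure is certainly inflated, or that it scores clinic moves as rejection of RE-PACT. Section 3 does not define drop-out closely enough for the first, and its denominator includes controls, who receive no intervention. Section 7.2 also records the reason for each discontinuation, so departures can be separated at reporting.
- Missing the criterion prompts adjustment between waves, and section 9.4.2 makes the final analysis descriptive.

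**Conclusion.** The point holds as an inconsistency with a practical consequence. Leaving the program ends enrolment and, on the plain reading, is recorded as loss to follow-up, without asking whether the family can and will continue. Families who stop the intervention are followed. The 6-month intention-to-treat estimate then depends on missing-data assumptions that further follow-up could partly replace.

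For the clinical outcome the likely loss is small: under 4% of person-months with 7 leavers at mid-study, if earlier time is kept. Bias is conditional on departure being related to both arm and risk, and it cannot be sized from the documents.

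For the drop-out criterion the effect could decide pass or fail, but only if departure counts, which section 3 leaves open. The limits of 8 in 90 and 0 in 10 are firm. Everything beyond them rests on assumed departure and drop-out rates, and within those assumptions the measure can pass (7.8%) or fail (12.2%).

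**What to change.** Reconcile sections 3, 7.1, 7.2, 7.3 and 9.3 as follows.

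- State that leaving the program ends intervention delivery only. Continue the 6-month caregiver assessment and outcome collection while the family consents and can be reached.
- Collect caregiver-reported hospitalizations for leavers, confirmed from records where the signed authorisation allows.
- Count person-months to last contact.
- Reserve loss to follow-up for families who cannot be contacted, and make clear which limbs of section 7.3 the contact condition covers.
- Say in section 3 whether program departure counts as drop-out, and report it as a separate line by arm and wave.
- Align the program named in section 7.2 with the entry programs in section 4.1.

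The cost is protocol wording plus one telephone or online questionnaire per leaver, with a records request where permitted. The downside is that a few outcomes will rest on caregiver report rather than chart abstraction. Flag the source of each such outcome, and check the results without them in a sensitivity analysis.

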3 OBJECTIVES AND ENDPOINTS

OBJECTIVES	ENDPOINTS			JUSTIFICATION FOR ENDPOINTS	PUTATIVE MECHANISMS OF ACTION
Primary					
To establish feasibility, acceptability, and fidelity of RE-PACT in 90 children with severe CP.	MEASURES	MEASURE DETAIL	SUCCESS DEFINITION		
	FEASIBILITY		n=90		
	Recruitment	Days to enroll target, mean	<14		
	Intervention onset	Days between randomization and “time zero” intervention activities, mean	<7		
	Intervention time	Time logged (minutes) for action planning and for coaching activities, mean			
	Intervention costs	Mileage / travel costs; Personnel salary; Training; Other incurred costs, total			
	Intervention triggers	Number per patient (annualized); respiratory and non-respiratory focused			
	Data infrastructure	Data collection reliability; Coordination at UW, Data use agreements / IRBs			
	ACCEPTABILITY				
	Enrollment	Enrollment rate (# of patients enrolled / # approached)	>80%		

OBJECTIVES	ENDPOINTS			JUSTIFICATION FOR ENDPOINTS	PUTATIVE MECHANISMS OF ACTION
	Consent refusal	Categorized reasons for refusal			
	Loss, Drop out	Rate of drop out (active or passive) before 6 months (# drop out / # enrolled)	<10%		
	Action plan, Coaching, texting satisfaction	Do caregivers use the action plan, coaching and texting (why / why not); How could it be improved; Would caregivers recommend this to another family? (why / why not)			
	FIDELITY				
	Enrollment duration	Time (months) of participant enrollment in the study, mean	6		
	Action plan creation	# respiratory and overall action plans per patient; Action plan focus areas	≥1		
	Coaching – home or virtual visit	Success rate (# visits completed / # expected); stratify by trigger (hospitalization vs confidence rating)	>80%		

OBJECTIVES	ENDPOINTS			JUSTIFICATION FOR ENDPOINTS	PUTATIVE MECHANISMS OF ACTION
	Coaching – phone calls	Success rate (# phone calls completed / # expected); stratify by trigger (hospitalization vs confidence rating); respiratory and non-respiratory	>80%		
Secondary					
To establish effect size of RE-PACT.	Severe respiratory illness, defined as respiratory diagnoses requiring hospitalization. Respiratory diagnoses includes discharge diagnosis of any of the following: asthma, pneumonia (community or hospital acquired), bronchiolitis, influenza, upper or lower respiratory tract infection,				

OBJECTIVES	ENDPOINTS	JUSTIFICATION FOR ENDPOINTS	PUTATIVE MECHANISMS OF ACTION
	tracheitis, aspiration pneumonia/pneumonitis, chronic lung disease, respiratory failure.		

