RE-PACT involves action planning and health coaching to prevent and manage respiratory illness, as well as weekly text messaging surveillance of caregiver confidence for their child to avoid a hospitalization. All intervention families will receive respiratory illness action plans at study entry. Action plan content will be consistent with standard clinical care guidelines and will not differ from the recommendations of the child's clinical care team. Health coaching focuses on managing medications, understanding and responding to red flags, keeping patient-centered records, maintaining timely follow-up with primary or specialty care. Coaches focus on skill transfer to parent caregivers, achieved through structured face-to-face or virtual telehealth coaching and phone follow-up over a 2-week period. Just-in-time action planning and coaching activities are triggered by caregiver text message responses indicating low confidence (rating ≤ 4 on 1-10 scale) to avoid a hospitalization. The usual care, active control group will continue to receive comprehensive care coordination and medical management.

Study participants will be randomly assigned to receive usual care through the complex care clinical program, or the study intervention, RE-PACT. Random allocation will be concealed to research staff conducting recruitment and will use a 1:1 allocation with random block sizes of 2 and 4. Block randomization will be achieved with a computer-generated random number list prepared by the study

biostatistician having no clinical involvement in the trial. Randomization will be stratified by site to account for site-specific study characteristics.

RE-PACT will be run through three successively larger 6-month trials (“waves”), allowing ongoing protocol refinement according to pre-specified definitions of success for measures of feasibility, acceptability and fidelity. Each wave has a specific protocol refinement focus: Wave 1 – onboarding/training, recruitment, data collection; Wave 2 – randomization and intervention activities; Wave 3 – rapid enrollment and conducting all protocol activities with high-fidelity.

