4.3 JUSTIFICATION FOR INTERVENTION

Justification for the mode of intervention delivery. RE-PACT uses a dynamic Just-in-Time Adaptive Intervention (JITAI) design.¹⁷ Though causes of respiratory illness in severe CP are modifiable, they are also broad and require distinct responses, even for the same child over time. RE-PACT's design addresses child and family changing needs. Managing crises with just-in-time action planning and bringing coaching directly to families breaks down barriers between home and clinical settings precisely when it matters most. This approach is innovative since we tailor the intensity of response (e.g., phone call, clinic visit, etc.) to family- and illness-specific needs. The adaptive nature of the intervention ensures it meets caregiver needs for that particular illness, whether requiring purely respiratory or a mix of respiratory and non-respiratory chronic disease management (e.g., seizures, feeding intolerance, etc.). The number and frequency of contacts is rooted in prior research using a related trial as well as feedback from families pilot-testing our texting tool. There is no minimum-acceptable participation in, or exposure to the intervention since the study is designed to assess feasibility, acceptability, and fidelity, i.e., varying rates of participation will be a relevant endpoint in itself.

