Just-in-time Adaptive Coaching Intervention Response. Coaching is accomplished by adapting PACT, which was initially adapted from the Care Transitions Intervention® (CTI),⁵⁰ to the pediatric population. The focus is: (1) medication self-management, (2) patient-centered records maintained by families, (3) timely follow-up, and (4) "red flags" and instructions how to identify/respond to them (i.e., action plans). Face-to-face visits are typically at the family's home; however, a neutral or "virtual" (telephone) visit is an option. Coaches review the four components, elicit goals, and focus coaching activities on needs identified by families. Phone calls discuss progress toward goals. This coaching approach provides the structure for JITAI activities.

Control Group. Those participants randomized to the control group will be provided usual care through the comprehensive clinical program at their children's hospital. They will also complete pre- and post-study assessments.

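### Section 7.2 allows one-arm replacement after randomisation, and nothing says that replaced families stay in the intention-to-treat set and in the drop-out and fidelity counts

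*Combined protocol and SAP*

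**What the plan says.** Section 7.2 of the protocol separates two kinds of loss. For families who never start, "Subjects who sign the informed consent form and are randomized but do not receive the study intervention may be replaced". Families who receive the intervention and "subsequently withdraw, or are discontinued from the study, will not be replaced". The reason for every withdrawal goes on a case report form.

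Section 4.1 shows what the study intervention is: "Study participants will be randomly assigned to receive usual care through the complex care clinical program, or the study intervention, RE-PACT". Section 6.1.1 describes the other arm: "Those participants randomized to the control group will be provided usual care".

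Three other places bear on the rule:

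- Section 4.3: "There is no minimum-acceptable participation in, or exposure to the intervention", because "varying rates of participation will be a relevant endpoint in itself".
- Section 3 makes drop-out a primary acceptability measure, "Rate of drop out (active or passive) before 6 months (# drop out / # enrolled"), with success set below 10%. Enrolment duration (mean 6 months) and action plans per patient (at least 1) are primary fidelity measures.
- Section 9.3: "we will use an intention-to-treat analysis approach". It defines no analysis set and does not mention replaced families.

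Section 9.2 fixes the total at 90, in waves of 10, 20 and 60. Under Section 8.1 the protocol is adjusted between waves for any measure that falls short of its definition of success.

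**The concern.** A family that consents, is randomised to RE-PACT and never starts is one of the outcomes this pilot exists to observe. Section 7.2 allows another family to take its place. No matching event exists in the control arm, so the rule selects on something that happens after randomisation, in one arm only, and is plausibly related to acceptability.

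Two things are at stake. The first is the primary measures, where never-starters could disappear from the drop-out, enrolment-duration and action-plan figures. The second is the between-arm comparison behind the effect size for the later trial, which would no longer compare the groups as randomised.

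**Working it through.** The plan gives no figure for never-starters or replacements, so there is nothing of its own to reproduce. The check has three steps.

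**1. Which arm does the rule reach?** Section 4.1 sets RE-PACT against usual care, and Section 6.1.1 gives controls usual care. Taken literally, no control ever receives the study intervention and every control would be replaceable, which cannot be meant. The workable reading is the intervention arm only.

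**2. Does a replaced family leave the counts?** No section says so, and none says it stays. A fixed total of 90 points toward leaving, since a family can be replaced within 90 only by giving up its place. Intention-to-treat, and a drop-out denominator based on the number enrolled, point toward staying. Both branches therefore need numbers.

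**3. Effect on the drop-out measure.** Let k be the never-starters in the intervention arm and d the other drop-outs. The rate is:

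- no replacement: (k + d)/90
- replaced and removed: d/90
- replaced but kept: (k + d)/(90 + k)

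Illustrative counts, assumed:

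| k | d | No replacement | Removed | Kept |
|---|---|---|---|---|
| 3 | 6 | 9/90 = 10.0%, fails | 6/90 = 6.7%, passes | 9/93 = 9.7%, passes |
| 7 | 4 | 11/90 = 12.2%, fails | 4/90 = 4.4%, passes | 11/97 = 11.3%, fails |
| 2 | 4 | 6/90 = 6.7%, passes | 4/90 = 4.4%, passes | 6/92 = 6.5%, passes |

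By wave, with no other drop-out:

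- Wave 1, one never-starter: 1/10 = 10.0% (fails), removed 0/10, kept 1/11 = 9.1% (passes).
- Wave 2, two never-starters: 2/20 = 10.0% (fails), removed 0/20, kept 2/22 = 9.1% (passes).

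For the chance of meeting <10%, assume that each intervention family never starts with probability p and that 5% of families in both arms drop out later:

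- No replacement: k is binomial(45, p), d is binomial(90 − k, 0.05); pass if k + d ≤ 8.
- Removed: d is binomial(90, 0.05); pass if d ≤ 8.
- Kept: k is negative binomial (never-starters met before 45 families start), d is binomial(90, 0.05); pass if (k + d)/(90 + k) < 0.10.

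| p | No replacement | Removed | Kept |
|---|---|---|---|
| 5% | 0.78 | 0.96 | 0.84 |
| 10% | 0.48 | 0.96 | 0.52 |
| 20% | 0.07 | 0.96 | 0.06 |

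Removal makes the result blind to p. Keeping the families shifts the chance only slightly. The shift reverses at 20%, where replacements themselves often fail to start.

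**Effect on the rate ratio if families are removed.** Suppose there is no true effect, a fraction p of families are never-starters, and their event rate is m times that of starters. The control arm retains its equivalent families and the intervention arm does not, so the expected control-to-intervention ratio is (1 − p) + p·m. For m from 0.5 to 3:

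- p = 10%: 0.90 + 0.05 = 0.95, up to 0.90 + 0.30 = 1.20.
- p = 20%: 0.80 + 0.10 = 0.90, up to 0.80 + 0.60 = 1.40.

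**The case against.** A reader might infer that the plan removes acceptability failures and breaches its own intention-to-treat rule. The documents do not support that as a statement of fact. The replacement sentence is permissive and can be read as a recruitment rule. Section 9.3 adopts intention-to-treat precisely because the intervention depends on parent adherence. Section 8.1 treats randomisation and enrolment as one event, so a randomised never-starter is already in the drop-out denominator as defined. Section 7.1 keeps and assesses families who stop part of the intervention. All of this stands, and it is why the point is conditional on how replaced families are handled.

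Further limits also stand:

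- Replacement with retention has a purpose: it restores the number of families exposed, which matters when judging delivery.
- The onset measure is unaffected. A never-starter has no time-zero date and is absent from that mean whether or not it is replaced. Refusals before consent are counted separately.
- The pool may be small. Willingness to text is screened, texting starts the Monday after enrolment, and if a first text counts as receipt few families would qualify. If the action plan counts (due within a month), more would. The protocol does not define receipt.
- The clinical comparison is secondary and declared underpowered, and the primary measures are descriptive.

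These points limit the size of the problem but do not remove it. Section 4.3 and the replacement rule still pull in opposite directions, and no sentence settles where replaced families are counted.

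**Conclusion.** The concern holds in conditional form. Section 7.2 permits replacement that is post-randomisation and, in practice, confined to one arm. It conflicts with Section 4.3 and leaves the intention-to-treat set and the primary denominators open.

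If replaced families leave, the comparison is not intention-to-treat, and drop-out, enrolment duration and action-plan creation lean toward success. At an assumed 10% never starting and 5% later drop-out, the chance of meeting the drop-out target rises from 0.48 to 0.96. If they stay, the effect is modest (0.48 to 0.52), although in Waves 1 and 2 it can turn a fail into a pass and so miss a protocol adjustment.

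All these probabilities, and the rate-ratio ranges, rest on assumed rates. At low counts all three treatments of the data pass. The plan should be changed because the rule is explicit, touches primary measures and is easily corrected; an actual breach of intention-to-treat has not been shown.

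**What to change.** Delete the replacement sentence from Section 7.2. In Sections 9.3 and 3, state that every randomised family stays in its assigned arm for the intention-to-treat analysis and in every drop-out and fidelity denominator that applies to that arm.

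If more families are enrolled, they should be newly randomised through the site-stratified list, should not count as substitutes, and should be reported separately from the originally randomised families when drop-out is judged against <10%. Define what counts as receiving the three-part intervention, so that never-starters can be identified and reported.

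The cost is a few sentences. The drop-out figure may be less favourable and could miss its target, and the number of families exposed to RE-PACT may fall below 45 unless additional families are randomised.
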